All personal data provided by the patient is absolutely confidential and will be treated in accordance with the General Law on the Protection of Personal Data Held by Private Parties. Participants will not be identified in any reports or publications resulting from this study. In all documents, including laboratory test results, the participant will be identified with a code that includes a number and their initials to ensure the anonymity of their data. The personal data provided by the participant may only be reviewed by the principal investigator, a regulatory entity, or an auditor if verification is necessary. Furthermore, we guarantee that the processing of this data will be legitimate, transparent, and appropriate, and always within the purposes established for this project. When the blood sample is collected, the participant will be assigned a unique code, which will be used to label the blood sample tubes.

The researcher in charge of the study is responsible for the processing and protection of the personal data obtained and will ensure that they are protected in accordance with the provisions of the General Law on the Protection of Personal Data Held by Private Parties and the General Law on the Protection of Personal Data Held by Obligated Subjects. The personal data requested will be used exclusively for the purposes outlined in this project, thereby ensuring compliance with data protection regulations and safeguarding the privacy of individuals, both in the private and public spheres, in accordance with applicable laws.

All participants will receive a brochure entitled "Comprehensive Wellness for Patients with Rheumatoid Arthritis," prepared by nutrition and fitness experts, which includes healthy eating

recommendations and physical activity routines tailored to their condition. They will also receive a workshop on physical activity at the Rheumatology Service facilities and nutritional guidance.

In case the patient requires medical attention due to an adverse effect of vitamin E supplementation, he/she will be asked to contact the principal investigator to arrange care in a hospital (agreement in process with the FELMAN Hospital, Annex 18).

This study has been approved by the Research and Ethics Committees of the Fray Antonio Alcalde Civil Hospital (Annex 15). Once the protocol is approved by the committees responsible for evaluating research projects at CUCS, this project will be registered in Clinical Trials, for which information has already been requested and the Workshop for Strengthening Good Practices in Clinical Trials was attended, organized in collaboration with the Good Clinical Trials Collaborative (GCTC) and The Global Health Network (TGNH).

7. Methodology

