UNIVERSITY OF GUADALAJARA
UNIVERSITY CENTER FOR HEALTH SCIENCES
BIOMEDICAL SCIENCES RESEARCH INSTITUTE

Project title:

**“Evaluation of the effect of vitamin E (α -tocopherol)
supplementation on clinical activity and inflammation in patients
with rheumatoid arthritis”**

NCT: 06915701

April 7, 2025

Summary

Background: Rheumatoid arthritis (RA) is a common autoimmune disease characterized by chronic inflammation and joint pain. The etiology of RA is multifactorial; genetic, environmental, hormonal, and epigenetic factors have been associated with it. Vitamin E is the term used for a group of tocopherols and tocotrienols, of which α -tocopherol has the greatest biological activity. The antioxidant and immunoregulatory effects of this vitamin are currently being investigated in chronic degenerative diseases, including RA.

General objective: To evaluate the effects of vitamin E (α -tocopherol) supplementation in patients with RA, as well as its relationship with the clinical activity and inflammation of the disease.

Materials and methods: A randomized, controlled, double-blind clinical trial was conducted. 46 volunteer patients with RA who met the selection criteria were recruited and divided into two groups of 23 patients: a control group (conventional treatment plus placebo) and an intervention group (conventional treatment plus 800 mg/day of vitamin E) for one month. A peripheral blood sample was obtained from both groups to be used for laboratory studies and to quantify proinflammatory cytokines IL-1 β , IL-6, and TNF- α using a multiplex assay. Serum α -tocopherol was quantified using gas chromatography (GC), and antioxidant capacity was also quantified using spectrophotometry and fluorescence at baseline and after one month. At the end of the study, the blinding will be unblinded, and both groups will be compared.

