6. To determine the antioxidant capacity before and after supplementation in both study groups
7. To associate vitamin E levels with clinical and inflammatory parameters in patients with RA

5. Hypothesis

There is an association between supplementation with Vitamin E (α -tocopherol) and the decrease in clinical activity and inflammation in patients with RA from Western Mexico

6. Methodological design

a) Type of study

- Randomized, controlled, double-blind clinical trial.
- Randomization: Simple randomization will be performed. The study will consist of two groups: control and intervention. Participants will be randomly assigned using a random selection process, using the OxMaR system (an acronym for Oxford Minimization and Randomization), a validated software. Randomization will be performed by a researcher independent of the project.
- Definition of patients:
- Female patients with RA will be included due to the prevalence and characteristics of the disease: a higher incidence in women and differences in clinical presentation, as they tend to present more severe signs and symptoms. Furthermore, the influence of hormonal factors is considered, given that female sex hormones have a significant impact on the modulation of the immune system. The study also seeks to improve the validity and applicability of the results through sample homogeneity, which reduces variability in treatment response associated with sex-related hormonal and genetic factors.
- Patients with vitamin E deficiencies (<15 mg/day) who are receiving conventional synthetic DMARDs (methotrexate, hydroxychloroquine, leflunomide, sulfasalazine, and their combinations) for more than one month. The intervention group will receive vitamin E at a dose of 800 mg/day, divided into two doses of 400 mg each. The control group will receive a magnesium oxide placebo at a dose of 200 mg/day. Participants will consume one capsule of vitamin E or placebo after their morning and evening meals.
- Patients receiving glucocorticoids will not be included, as current clinical guidelines advise against prolonged use of glucocorticoids, especially at high doses, and recommend limiting them to short-term bridging therapy in specific cases. Furthermore, it is suggested that treatment with these drugs may mask symptoms such as joint pain and decrease inflammatory parameters (acute phase reactants and proinflammatory cytokines).

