Liver and kidney diseases, overlap syndrome with other autoimmune diseases, coagulation disorders, pregnancy, consumption of supplements (iron, vitamin E and/or K), and medications such as aspirin, amlodipine, estrogens, glucocorticoids and medications used in the treatment of dyslipidemia in the last three months.

f) Elimination Criteria

Errors in supplement administration $\geq 20\%$: The treatment adherence form (Annex 14) will be used as the tool to be used, recording daily vitamin/placebo intake. Patients who fail to consume at least 80% of the total daily intake (48 capsules) will be eliminated from the study. Patients with adverse effects from the supplement (Annexes 15 and 16), pregnancy during the study, insufficient blood sample collection, and voluntary withdrawal of informed consent may be excluded.

g) Sample Size

The two-means statistical formula was used to calculate the sample size. To do this, the following data are required: Identify whether the hypothesis is unilateral or bilateral. Establish alpha and beta levels, and use them to determine the K value ($Z\alpha$ and $Z\beta$). The difference in measurements we would expect to find or want to be able to detect in our study ($\mu_1 - \mu_2$), the expected standard deviation for each group .

Calculations were performed using data from the 2001 clinical trial by Mona Helmy et al., resulting in a sample size of 19 patients plus a 20% increase to cover potential losses.

Data: Serum vitamin E levels: start: 0.64 mg/dL and end: 0.86 mg/dL

K value: 15.8 with a statistical power of 95%.

Standard deviation of vitamin E levels: start: 0.16 mg/dL and end: 0.18 mg/dL

Twenty-three patients were included in the control and intervention groups. Both groups had RA from the Rheumatology Service of the “Fray Antonio Alcalde” Civil Hospital in Guadalajara, Jalisco.

$$n = \frac{K(\sigma_1^2 + \sigma_2^2)}{(\mu_1 - \mu_2)^2}$$

Formula substitution:

$$n = \frac{15.8(0.16^2 + 0.18^2)}{(0.86 - 0.64)^2} = 18.93$$

$18.93 + 20\% \text{ in case of loss} = 22.7 = \mathbf{23 \text{ patients per group}}$

h) Variables

Independent variables

- Vitamin E

Dependent variables

- Inflammatory cytokines (IL-1 β , IL-6, and TNF- α). Antioxidant capacity (DPPH, ABTS, FRAP, and ORAC). Clinical course: DAS-28. Acute phase reactants: pCr and ESR. Autoantibodies: Anti-CCP and Rheumatoid factor.

Operationalization of variables			
Variable	Interrelationship	Nature	Indicator

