Vitamin E	Independent	Quantitative	$\mu\text{g}/\text{dl}$
Proinflammatory cytokines (IL-1 β , IL-6 and TNF- α)	Dependent	Quantitative	pg/ml
VSG	Dependent	Quantitative	mm/hr
C-reactive protein	Dependent	Quantitative	mg/l
Anti-CCP	Dependent	Quantitative	UR/ml
Rheumatoid factor	Dependent	Quantitative	IU/ml
Antioxidant capacity (DPPH, ABTS, FRAP and ORAC)	Dependent	Quantitative	$\mu\text{mol}/\text{L}$
DAS28	Dependent	Quantitative	Remission: < 2.6 Low activity: $\geq 2.6 < 3.2$ Moderate: $\geq 3.2 < 5.1$ High: ≥ 5.1

i) Biosecurity considerations

In this study, the guidelines established in the Mexican Official Standards, NOM-052-SEMARNAT-2005, will be applied. NOM-054-SEMARNAT-1993, NOM-003-SSA2-1993 and NOM-087-ECOL-SSA1-2002 which refer to the classification, handling, storage and disposal of hazardous waste, chemical reagents and biological-infectious, in order to guarantee the protection of people who are in contact with them and the environment (annex 1 and 2).

The biological material to be used will be whole blood, plasma, and serum. These biological samples will be obtained from RA patients in an in vivo experimental model (clinical trial). Blood sampling will be performed by trained personnel. Sharps will be disposed of in rigid red

polypropylene containers, based on the Classification of Establishments Generating Hazardous Biological-Infectious Waste in NOM-087-ECOL-SSA1-2002. This procedure will be performed by a PhD student and a Rheumatology resident in the Rheumatology Service of the Fray Antonio Alcalde Civil Hospital.

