7.1 Clinical Evaluation

7.2 Medical record

The clinical evaluation will be carried out by a rheumatology specialist, who will perform a general physical examination and apply clinical evaluation indices such as:

DAS28 Clinical Activity Index : This index measures disease activity in patients with rheumatoid arthritis (RA). It is calculated using four variables: the red blood cell sedimentation rate (ESR), the number of swollen joints, the number of painful joints (evaluating a total of 28 joints), and a visual analog pain scale. A mathematical formula is then applied, providing a score from 0 to 10. A value greater than 5.1 indicates high disease activity, a value less than 3.2 indicates low activity, and a value less than 2.6 indicates disease remission.

SDAI (Simplified Disease Activity Index): The SDAI is a more simplified disease activity index compared to the DAS28. It is based on five parameters: the number of swollen joints, the number of tender joints, the visual analogue pain scale score, the ESR (or C-reactive protein), and the patient's global status. The total score can range from 0 to 86, and like the DAS28, values above 26.0 indicate high disease activity, while values below 3.3 reflect disease remission.

CDAI (Clinical Disease Activity Index): The CDAI is similar to the SDAI, but differs in that it does not include laboratory measurements, i.e., it does not use ESR or C-reactive protein. It is

calculated by adding the following parameters: number of swollen joints, number of tender joints, the score on the visual analog pain scale, and the patient's overall condition. The total score ranges from 0 to 76, and like the SDAI, values less than 10 indicate disease remission, while values greater than 22.0 indicate high disease activity.

HAQ-DI (Health Assessment Questionnaire Disability Index): The HAQ-DI is a tool used to measure the level of physical disability in patients with chronic diseases, such as rheumatoid arthritis. It assesses a patient's functional ability in eight categories: dressing, bathing, eating, getting out of bed, walking, reaching, bending, and performing activities of daily living. Each category is scored from 0 to 3 (with 0 being no difficulty and 3 being maximum difficulty), and the total score is obtained by adding the scores for each category and dividing by the total number of categories assessed. A higher score indicates greater functional disability.

7.3 24-hour reminder

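### Simple randomisation of 46 patients leaves arm sizes and baseline DAS28 balance to chance, although the protocol states two groups of 23: a valid method that can be improved cheaply

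*Protocol*

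**What the plan says.** Protocol section 6 a), Type of study: "Randomization: Simple randomization will be performed". The same item adds "The study will consist of two groups: control and intervention" and says that an independent researcher will assign patients "using the OxMaR system (an acronym for Oxford Minimization and Randomization), a validated software". It names no block, stratification factor or minimisation factor.

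Two other places give group sizes. In the Summary the 46 patients are "divided into two groups of 23 patients". Section 6 g), Sample Size, says "Twenty-three patients were included in the control and intervention groups", after a calculation "resulting in a sample size of 19 patients plus a 20% increase to cover potential losses".

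DAS28 is an entry criterion in section 6 d) (3.2 or above, no upper limit) and a dependent variable in section 6 h). It is not used in the allocation. The table in 6 h) starts high activity at exactly 5.1, whereas section 7.2 says "A value greater than 5.1 indicates high disease activity".

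**The concern.** Simple randomisation is a separate coin toss for each patient, so it does not deliver two groups of a set size. With 46 patients the split can drift noticeably. Chance can also put more of the highly active patients in one arm. DAS28 matters most here because clinical activity is in the title, the hypothesis and specific objective 4. Restricting entry to women with early disease and no glucocorticoids narrows the population but does not balance DAS28 between the arms.

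At stake is avoidable chance imbalance, and with it a result that is harder to interpret if the arms start out visibly different. Allocation cannot be redone afterwards, so the time to consider this is before it starts.

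**Working it through.** **Inputs from the protocol.** N = 46, two arms; 1:1 is inferred from the equal groups. From 6 g): means 0.64 and 0.86 mg/dL, SDs 0.16 and 0.18 mg/dL, K = 15.8, power 95%, and a 20% increase for losses.

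**The plan's own figure.** n = 15.8 × (0.16² + 0.18²) / 0.22² = 15.8 × 0.0580 / 0.0484 = 18.93. Then 18.93 × 1.2 = 22.7, so 23 per group. This reproduces.

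**Arm sizes.** With X ~ Binomial(46, 0.5):
- P(X = 23) = C(46,23)/2⁴⁶ = 0.117.
- P(an arm of 18 or fewer) = 2 × P(X ≤ 18) = 0.184.

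**Power.** The protocol gives no numerical alpha. K = 15.8 with 95% power implies √15.8 − 1.645 = 2.33, a two-sided alpha of about 0.02. For a pooled t-test with difference 0.22 and SD √(0.0580/2) = 0.170:

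| Split | Power |
|---|---|
| 23/23 | 97.2% |
| 18/28 | 96.5% |
| 15/31 | 95.1% |
| 19/19 | 93.4% |
| Average over all splits of 46 | 96.9% |

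**Baseline DAS28.** At 23/23 the difference in baseline means has standard error √(2/23) = 0.295 SD. P(|difference| > 0.5 SD) = 2 × (1 − Φ(0.5/0.295)) = 2 × (1 − Φ(1.70)) = 9.0%. Averaged over the random splits it is 9.4%.

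**Consequence when there is no true effect.** I simulated 20,000 trials per setting under simple randomisation, with a normal baseline, alpha 0.05 and assumed baseline-to-outcome correlations of 0.4, 0.6 and 0.7.
- Overall rejection is about 5%, adjusted or not.
- In the trials with a gap above 0.5 SD, an unadjusted final-value test rejects in about 11%, 21% and 24%. A baseline-adjusted test rejects in about 5%.
- In the remaining 91% or so, the unadjusted test rejects in about 3% to 4%, which is how the overall rate stays at 5%.

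**Restricted allocation.** In simulations of blocks of 4 and 6 stratified by DAS28 category, with 30%, 50% or 70% of patients assumed in the high category:
- the smaller arm has at least 21 patients in 99.99% of trials;
- the proportions in the high category never differ by more than 13 points;
- a mean gap above 0.5 SD occurs in 0.7% to 1.3% of trials (run at 50% and 30% high);
- exactly 23/23 occurs in about 55% to 56%.

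Minimisation on DAS28 category, with probability 0.8 of the balancing arm, gives 23/23 in about 52% and a smaller arm of at least 21 in 99.4%.

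**Completers.** Chance that at least one arm ends with fewer than 19, with independent losses. Blocks are approximated as 55.5% at 23/23 and otherwise 22/24.

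| Loss | Simple | Stratified blocks | Fixed 23/23 |
|---|---|---|---|
| 5% (assumed) | 32% | 2% | 1% |
| 10% (assumed) | 51% | 16% | 14% |
| 20% (protocol) | 88% | 76% | 75% |

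At the protocol's own 20%, even a perfect split leaves 23 × 0.8 = 18.4 expected completers per arm. There the loss allowance matters more than the allocation method.

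**The case against.** The strongest reply is that nothing here is broken. Simple randomisation is unbiased, and the test's error rate already allows for chance imbalance. Unequal arms cost almost no power. Twenty-three per group comes out of a sample-size formula and reads naturally as a target, and the proposed methods give exactly 23/23 in only 52% to 56% of trials. The raised rejection rate applies only to the 9% or so of trials with a large gap, and only to an unadjusted test, which the protocol nowhere specifies. All of this stands, and it limits the weight of the point. What remains is that the protocol describes its groups as fixed, and that restricted allocation is cheap and usual at this size.

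Three stronger readings are tempting, and the document does not support them:

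- **That the allocation mode is unstated or contradictory.** Section 6 a) says simple. The software's full name covers randomisation as well as minimisation, and the absence of listed minimisation factors fits simple allocation.
- **That an arm below 19 is a failure.** Nineteen per group presumes equal arms; 18/28 has more power than 19/19 because it has eight more patients. The 18.4% describes arm sizes and is not a chance of an underpowered trial.
- **That the trial's false-positive rate is 11% to 24%.** Those are conditional rates; the overall rate is 5%.

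**Conclusion.** The point holds as a modest, optional improvement. Allocation as written gives the stated 23/23 in 11.7% of trials and an arm of 18 or fewer in 18.4%, and leaves a baseline DAS28 gap above 0.5 SD in about 9%. Stratified blocks would cut that last figure to about 1%. Validity and power on the vitamin E inputs are not in question, and adjusting for baseline DAS28 removes most of the consequence whichever method is used.

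The arm-size figures are exact, given 46 patients and independent 1:1 assignment. The power figures rest on the alpha implied by K. The DAS28 figures rest on an approximately normal baseline and on assumed correlations and category proportions, none of which the protocol gives. How the trial will be analysed may be settled in a statistical analysis plan that is not at hand, so no fault is found there.

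**What to change.** **Allocation (section 6 a).** Replace simple randomisation with one of:
- 1:1 permuted blocks of varying, undisclosed size, stratified by baseline DAS28 category (moderate or high); or
- the named system's minimisation, with a random element, on DAS28 category.

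**Stratum cut.** Sections 6 h) and 7.2 classify a DAS28 of exactly 5.1 differently. Reconcile them and use a single cut.

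**Analysis.** Include baseline DAS28 in the model. If the statistical analysis plan already does so, nothing more is needed.

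**Group sizes (Summary and section 6 g).** Call 23 per group a target.

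**If allocation has begun.** Keep the method in use, make the target wording change, and specify the baseline adjustment before unblinding.

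**Cost.** A few sentences, and one value already needed for eligibility. The downside is practical: DAS28, including the ESR result, must reach the independent researcher before allocation, and the factor must be carried into the analysis.

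### Section 6 f) removes randomised patients for low capsule intake or adverse effects, and no text shown keeps their one-month assessment

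*Protocol*

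**What the plan says.** The Protocol, section 6 f) Elimination Criteria, has two rules that act after random assignment.

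- **Adherence, mandatory:** "Patients who fail to consume at least 80% of the total daily intake (48 capsules) will be eliminated from the study". It applies to both arms, because the adherence form is described as "recording daily vitamin/placebo intake". The same paragraph opens by setting the ground for elimination at administration errors of 20% or more.
- **Adverse effects, discretionary:** "Patients with adverse effects from the supplement (Annexes 15 and 16") head a list of grounds that ends with "voluntary withdrawal of informed consent may be excluded".

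The Summary describes the comparison only in general terms: "At the end of the study, the blinding will be unblinded, and both groups will be compared". Section 6 g) Sample Size treats losses as a matter of number, "resulting in a sample size of 19 patients plus a 20% increase to cover potential losses", which gives 23 per group.

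Section 6 a) has patients with adverse events followed until the event resolves, and it holds the blind until supplementation and data collection are over. Section 7.5 Patient Diary compares leftover capsules with the expected number and specifies no interim count.

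**The concern.** Randomisation makes the two arms comparable at baseline. Removing patients for what happens afterwards can undo this. Low intake and adverse effects may both be related to how a patient is doing, and they may be more frequent in one arm, since the capsules hold different substances (vitamin E or magnesium oxide). If removal is related to outcome and differs between arms, the contrasts in DAS28, cytokines and serum vitamin E no longer compare the groups that were randomised.

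This is more than an analysis set left unnamed, which a statistical analysis plan could supply. The protocol orders removal from the study. A later plan can use one-month values that were collected, but it cannot recover values from a patient who was removed before the visit.

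The adherence rule also contradicts itself at its boundary and in its unit, so two readers could classify the same patient differently.

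**Working it through.** **1. The protocol's own figures.** Section 6 g) gives "Serum vitamin E levels: start: 0.64 mg/dL and end: 0.86 mg/dL", SDs of 0.16 and 0.18 mg/dL, and "K value: 15.8 with a statistical power of 95"%.

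- n = 15.8 × (0.16² + 0.18²) / (0.86 − 0.64)² = 15.8 × 0.0580 / 0.0484 = 18.93. Then 18.93 × 1.2 = 22.7, so 23. This reproduces.
- The loss allowance is 23 − 19 = 4 per group (17.4%).
- K: (2.326 + 1.645)² = 15.77. This fits a one-sided 1% test or, equally, a two-sided 2% test, with 95% power. The protocol states neither alpha nor sidedness. A two-sided 5% test would give 12.99.

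**2. The adherence boundary.** Section 6 a) has two capsules a day. Over 30 days that is 60 capsules, and 80% of 60 is 48. So 48 is a share of a 30-day total, not of a daily intake (28 days: 44.8; 31 days: 49.6). A patient who takes exactly 48 of 60 has missed 12, or 20%. The wording on errors of 20% or more removes her; the wording on at least 80% keeps her.

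**3. Possible bias when there is no true effect.** The documents give no removal rates and no correlation of removal with outcome, so these are assumed. If a proportion p of an arm is removed, and removal has correlation ρ with a worse outcome (normal model), the retained mean shifts by ρ·φ(z_p)/(1 − p) SD. The bias is the difference between arms.

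| Removed, arm A / arm B | φ(z_p)/(1 − p), A / B | Shift, ρ = 0.3 | Shift, ρ = 0.5 | Standard error |
|---|---|---|---|---|
| 20% / 5% | 0.350 / 0.109 | 0.072 SD | 0.121 SD | 0.316 SD |
| 4/23 / 1/23 | 0.311 / 0.096 | 0.064 SD | 0.107 SD | 0.313 SD |
| equal | equal | 0 | 0 | – |

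The shift favours the arm that loses more patients. If those removed would have done better, the sign reverses.

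Simulated error of a two-sided 5% pooled t-test (100,000 runs per case, 23 randomised per arm): about 5.4% to 5.6% at ρ = 0.3 and 6.2% to 6.6% at ρ = 0.5. With equal removal, or ρ = 0, it is about 5%.

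**4. Cost of keeping everyone.** The start and end values are read as a between-arm difference, as the protocol's formula does. The average SD is √(0.0580/2) = 0.1703, so d = 0.22/0.1703 = 1.292. If 4 of 23 supplement patients gain nothing:

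- mean difference: 0.22 × 19/23 = 0.182;
- added variance in that arm: (4/23)(19/23)(0.22²) = 0.00695;
- pooled SD: √(0.0290 + 0.00695/2) = 0.180, so d = 1.008.

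Power from the noncentral t:

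| Case | Two-sided 5% | Two-sided 2% or one-sided 1% |
|---|---|---|
| 23 vs 23, all gain fully | 99% | 97% |
| 19 vs 19, adherent only | 97% | 93% |
| 23 vs 23, 2 supplement patients gain nothing | 97% | 92% |
| 23 vs 23, 4 supplement patients gain half | 97% | 93% |
| 23 vs 23, 4 supplement patients gain nothing | 92% | 84% |

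The protocol gives no effect sizes for DAS28 or cytokines, so dilution there cannot be computed.

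**The case against.** The strongest reply is that most of this belongs to a statistical analysis plan, which may exist and is not shown. That plan could define an all-randomised comparison. This stands for any values that are collected, and so the point rests on the removal rule and not on the absence of a named analysis set.

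A second reply is that data loss under the mandatory rule may be small. The threshold is a one-month total and no interim count is specified, so many low-adherence patients could already have been measured when the shortfall is found. This also stands. Irrecoverable loss mainly concerns patients removed early.

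Third, the methodology diagram and the annexes on adherence and adverse events are not shown and might provide for the visit. That limits confidence in an absence. The nearest text that is shown, in section 6 a), is safety follow-up and does not provide for the one-month efficacy measurements.

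A reader might infer three stronger claims that the documents do not support:

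- *The rule favours the supplement.* It covers both arms under blinding, so no direction can be given. Blinding guards against knowing selection but does not make removal equal between arms.
- *Every patient with an adverse effect is dropped.* That ground is discretionary, and section 6 a) describes symptomatic treatment for mild or moderate events.
- *The trial uses a one-sided 1% test whose error is multiplied.* K fits two-sided 2% just as well, so no one-sided error figure should carry weight.

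**Conclusion.** The point holds, as something that should be fixed, with medium confidence. Section 6 f) orders removal on one post-randomisation ground and permits it on another, and nothing shown restores the randomised comparison. The sample-size allowance does not address this.

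The likely size is modest: about 0.06 to 0.12 SD against a standard error of 0.31 to 0.32 SD, with two-sided 5% error of about 5.4% to 6.6%. This rests on assumed unequal removal and an assumed correlation of 0.3 to 0.5 with outcome. It vanishes if removal is equal by the same mechanism or unrelated to outcome.

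The inconsistent boundary follows from the protocol's wording and, for the meaning of 48, from a 30-day month. Pregnancy, insufficient samples and withdrawal of consent are outside this point.

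**What to change.** In section 6 f), for low adherence and adverse effects, replace elimination or exclusion with continued follow-up: each such patient who has not withdrawn consent is asked to attend the one-month assessment and blood sample. State that the main comparison takes all randomised patients in their assigned arm. Use the 80% rule only for a secondary per-protocol set, fixed before unblinding, with a single boundary expressed as a one-month capsule total. Rules for stopping capsules stay with the investigators.

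The cost is protocol wording, a few extra visits and some dilution. In the worst case shown (4 of 23 supplement patients gaining nothing), power for serum vitamin E is about 92% at two-sided 5%, or 84% at two-sided 2% or one-sided 1%. Both are below the stated 95%. The protocol should say so, give its alpha and sidedness, and confirm whether 23 per group is still acceptable.
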